5.3 Lifestyle Considerations

Participants must abstain from donating blood and plasma from the time of informed consent, and for 16 weeks (5 half-lives) after final administration of study intervention.

5.3.1 Meals, Dietary Restrictions, and Caffeine

- 1 Participants should avoid eating a large meal for at least 2 hours prior to all spirometry, AO and FeNO assessments at the site.
- 2 Participants should not eat or drink one hour prior to having FeNO assessment.
- 3 During each dosing session, participants will abstain from ingesting caffeine- or xanthine-containing products (eg, coffee, tea, cola drinks, and chocolate) for 4 hours prior to in-clinic spirometry.

5.3.2 Activity

- 1 Participants should avoid engaging in strenuous exercise for 2 hours prior to all spirometry, AO and FeNO assessments, both in clinic and at home.
- 2 Participants should avoid showers/bathing and any activity that will cause heavy perspiration whilst wearing the cough monitor, as the cough monitor must not come into contact with water.

5.4 Screen Failures

Note: "Enrolled" means a participant's, or their legally acceptable representative's, agreement to participate in a clinical study following completion of the informed consent process.

Screen failures are defined as participants who consent to participate in the clinical study but are not subsequently randomly assigned to study intervention. A minimal set of screen failure information is required to ensure transparent reporting of screen failure participants to meet the Consolidated Standards of Reporting Trials (CONSORT) publishing requirements and to respond to queries from regulatory authorities. Minimal information includes demography, screen failure details, eligibility criteria, and any SAE.

Individuals who do not meet the criteria for participation in this study (screen failure) may be rescreened, if there is reason to believe the reason for screen failure was temporary. Only one rescreening per participant is allowed in the study. The timing of the rescreening should be determined by the PI, taking into account the initial reason for screen failure. Prior to rescreening, participants must be reconsented and will retain their original SID number.

6 STUDY INTERVENTION

Study intervention is defined as any investigational intervention(s), marketed product(s), placebo, or medical device(s) intended to be administered to a study participant according to the study protocol.

6.1 Study Interventions Administered

Table 5 Study Interventions

Intervention Name	MEDI3506	Placebo
Type	Biologic	Drug
Dose Formulation	CCI [REDACTED]	CCI [REDACTED]
Unit Dose Strength	CCI mg/mL	Not applicable
Dosage Level	CCI mg, CCI and CCI mg CCI	CCI
Route of Administration	SC injection	SC injection
Use	Experimental	Placebo
IMP and NIMP	IMP	IMP
Sourcing	AstraZeneca	AstraZeneca
Packaging and Labelling	Single vial kits with a unique number that is printed on all labels within the kit (ie, the outer carton label and the label of the vial within the carton). Labels will be prepared in accordance with GMP and local regulatory requirements.	Single vial kits with a unique number that is printed on all labels within the kit (ie, the outer carton label and the label of the vial within the carton). Labels will be prepared in accordance with GMP and local regulatory requirements.

GMP = good manufacturing practice; IMP = investigational medicinal product; NIMP = non-investigational medicinal product; CCI [REDACTED] SC = subcutaneous; w/v = weight/volume.

6.2 Preparation/Handling/Storage/Accountability of Interventions

- 1 Dispensation and dosing of study intervention should occur on the same day as allocation of study intervention by the RTSM system.
- 2 The investigator or designee must confirm appropriate temperature conditions have been maintained during transit for all study intervention received and any discrepancies are reported and resolved before use of the study intervention.
- 3 Only participants enrolled in the study may receive study intervention and only authorised site staff may supply or administer study intervention. All study intervention must be stored in a secure, environmentally controlled, and monitored (manual or automated) area in accordance with the labelled storage conditions with access limited to the investigator and authorised site staff.

- 4 MEDI3506 does not contain preservatives and therefore, any unused portion must be discarded.

The unblinded study intervention manager will select the appropriate kits allocated by the RTSM to prepare the participant's dose. The unblinded study intervention manager must ensure that only the unblinded team members have access to the areas of the pharmacy where the study intervention is being stored and prepared.

6.2.1 Study Intervention Inspection

Each vial allocated for dose preparation should be inspected. MEDI3506 and placebo are supplied as a clear to opalescent sterile liquids.

If there are any defects noted with the study intervention, the investigator and site monitor should be notified immediately. Refer to the Product Complaint section in the IMP manual for further instructions.

6.2.2 Dose Preparation Steps

No incompatibilities between MEDI3506 and plastics passing compatibility tests (ie, polypropylene and polycarbonate syringes) have been observed.

MEDI3506 and placebo do not contain preservatives and any unused portion must be discarded. Preparation of study intervention is to be performed aseptically. Total in use storage time from needle puncture of the study intervention vial to start of administration should not exceed 4 hours at room temperature or 24 hours at 2°C to 8°C (36°F to 46°F). If storage time exceeds these limits, a new dose must be prepared from new vials assigned by the RTSM.

A vial should be used only one time to prepare a single dose.

To prepare the participant's dose, the unblinded study intervention manager will select study intervention for administration according to the kit identification numbers assigned. A summary of the study intervention volumes required and syringes to prepare for SC dose administration in each treatment group is provided ([Table 6](#)).

Table 6 Study Intervention Dose Preparation

Contents of Vial(s)	Number of Kits	Volume Required	Syringes to Prepare	Size of Syringe	Total Volume of Study Intervention
CC mg MEDI3506 Treatment Group					
MEDI3506	C	CCI	CCI	CCI	CCI
CCI mg MEDI3506 Treatment Group ^a					
MEDI3506	C	CCI	CCI	CCI	CCI
Placebo	C	CCI	CCI	CCI	
Placebo Treatment Group					
Placebo	C	CCI	CCI	CCI	CCI

^a Do not mix MEDI3506 and placebo in the same syringe.

The dose preparation steps are, as follows:

- 1 Prepare the assigned MEDI3506 and/or placebo vials for the particular treatment group as per [Table 6](#).
- 2 Withdraw the required volume of MEDI3506 or placebo from each vial using a separate, appropriately sized syringe and a separate 18 to 20-gauge 1 to 1.5 inch needle, respectively.
- 3 Remove the 18-20-gauge needle. Replace with a capped 27-gauge 0.5 inch needle until administration.

6.2.2.1 Treatment Administration

The first day of dosing is considered Day 1 (SV4).

Female participants of childbearing potential, must have a negative urine pregnancy test prior to receiving each dose of study intervention.

MEDI3506 and placebo are not identical in appearance or viscosity. The syringes should be kept out of sight of all blinded persons, including the participant, to maintain the blind. Study intervention will be administered SC by unblinded site personnel via a 27 gauge 0.5 inch needle to the abdomen, back of the arms, or thigh. The 2 injections should be approximately 1 inch (2.5 cm) apart in the same anatomical region. The unblinded site personnel administering the dose will wipe the skin surface of the administration sites with alcohol and allow the skin surface to air dry. The skin will be pinched to isolate the SC tissue from the muscle. The needle will be fully inserted at a 45 degree angle into the SC tissue. The study intervention will be slowly injected (at least 5 seconds' duration is recommended). The area should not be massaged after injection.

It is advised that the site of injection be rotated so that the participant receives injections of study intervention in different anatomical regions from one visit to the next. In cases when rotation of the injection site is not feasible and/or the participant prefers not to rotate injection sites, the reason for not rotating the injection site should be documented in the source documents.

At each administration the time of the first injection and anatomical region used for both injections must be documented in the source documents.

6.2.2.2 Monitoring Dose Administration

After the administration of study intervention, vital signs will be assessed according to the SOA, and SC injection sites will be assessed for injection site reactions (Section 8.2.2) by the blinded study team. Participants should be monitored for a minimum of one to 2 hours after administration of study intervention (see Section 8.2.3).

As with any biologic product, allergic reactions to dose administration are possible. Therefore, appropriate drugs and medical equipment to treat acute anaphylactic reactions must be immediately available, and study personnel must be trained to recognise and treat anaphylaxis (Appendix H).

6.2.3 Accountability

The site's designated unblinded study intervention manager is required to maintain accurate study intervention accountability records. Upon completion of the study, copies of study intervention accountability records will be returned to AstraZeneca. All unused study intervention will be disposed of following site procedures and upon authorization by AstraZeneca, or will be returned to an AstraZeneca-authorized depot if a site is unable to dispose of unused study intervention.

6.3 Measures to Minimise Bias: Randomisation and Blinding

6.3.1 Methods for Assigning Treatment Groups

All participants will be centrally assigned to randomised study intervention using an RTSM. The randomisation will be stratified according to sub-study participation. Before each site is initiated, the log in information and directions for the RTSM will be provided. The RTSM will provide to the investigator(s) or pharmacists the kit identification numbers to be allocated to the participant at the dispensing visit. Routines for this will be described in the RTSM user manual that will be provided to each centre.

Study intervention will be dispensed at the study visits summarised in SOA or per SOC after data cut off.

6.3.2 Methods to Ensure Blinding

This is a double-blinded study in which MEDI3506 and placebo are not identical in appearance or viscosity. Neither the participant nor any of the investigator or sponsor staff who are involved in the treatment or clinical evaluation of the participants will be aware of the treatment received (ICH E9). Since MEDI3506 and placebo are not identical, study intervention will be handled by an unblinded study intervention manager at the site and will be administered by an unblinded study team member who will not be involved in the management of study participants. An independent study intervention monitor will also be unblinded to perform study intervention accountability. In the event that the treatment allocation for a participant becomes known to the investigator or other study staff involved in the management of study participants, AstraZeneca must be notified *immediately*. If the treatment allocation for a participant needs to be known to treat an individual participant for an AE (Section 6.3.3), the investigator must notify AstraZeneca *immediately*. The site will maintain a written plan detailing which staff members are blinded/unblinded and the process of study intervention preparation and administration used to maintain the blind.

MEDI3506 could reduce eosinophil counts in blood over time. As a precaution, eosinophil, basophil, and monocyte data from the haematology laboratory tests (Table 7) will not be communicated to blinded sponsor or site personnel during the treatment and follow-up periods.

To facilitate the in-stream analysis of PK and ADA samples, the randomisation schedule may be provided to limited personnel who have responsibility for analysing the samples. These unblinded sample analysts will not have any other involvement with the conduct of the study.

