1.3 Schedule of Activities

Once informed consent has been obtained, eDiary provision and training for site and home visits should occur first during SV1, followed by patient reported outcome (PRO) assessments. PRO assessments should be conducted first at all other visits. For all participants, in-clinic spirometry testing must be initiated between 6:00 AM and 11:00 AM during the screening or re-screening period, and randomisation visit (SV4). Whenever electrocardiograms (ECGs), vital signs, and blood draws are scheduled for the same nominal time, the order should be as follows: ECG, vital signs (vital signs can occur immediately after ECG using the same rest period), then blood draws. The timing of the first 2 assessments should be such that it allows the blood draw (eg, PK blood sample) to occur at the assigned nominal time. Whenever FeNO, airwave oscillometry (AO), and spirometry are scheduled for the same nominal time, the order should be as follows: FeNO, AO, then spirometry. Nasal sampling should be performed last, with nasal lining fluid collection performed before nasal epithelium collection (when both are scheduled). Urine samples may be collected at any time during the study visit (when scheduled). On days when investigational product is administered, all assessments should be performed pre-dose unless otherwise specified in the Schedule of Activities. Refer to Section 8 for additional information on assessment ordering (eg, pre-, post-dose or multiple timepoints within a visit). In the event that a clinical laboratory test result is not available from central laboratories during the screening period, see Section 8.2.7.

Table 1 Schedule of Activities: Screening Period

Visit Number	SV1	SV2	SV3
Procedure/Study Day	-35 to -28	-14 to -6	Visit no longer needed
Study Week	-4	-1	
Written ICF CCI /assignment of SID number	X ^a		
Written informed consent for future use and/or DNA analysis (optional)	X		
Verify eligibility criteria	X	X	
Demographics	X		
Baseline asthma assessments			
Provision of, and training on use of, home spirometry device and eDiary	X		
ACQ-6	X	X	
SGRQ		X	
SNOT-22 (comorbid CRS participants only)	X		
At-home eDiary completion and spirometry use	Twice daily throughout screening period		

Table 1 Schedule of Activities: Screening Period

Visit Number	SV1	SV2	SV3
Procedure/Study Day	-35 to -28	-14 to -6	Visit no longer needed
Study Week	-4	-1	
Assess adherence to at-home eDiary completion, spirometry, and SOC medication use		X	

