4.2.1.2 Secondary and Safety Endpoints

Safety, PK, and immunogenicity endpoints will be evaluated to inform risk-benefit analyses and determine optimal dosing regimen for MEDI3506 in asthma. PROs (ACQ-6 and SGRQ) reliably identify participants with uncontrolled asthma. CompEx is a composite score of asthma control composed of data gathered using an eDiary and asthma exacerbation reporting that has predictive value in assessing whether an intervention reduces asthma exacerbations of asthma (Fuhlbrigge et al 2017). FeNO is a reliable quantitative tool to assess changes in asthma inflammation over time.

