6.5.3 Medication Withhold Periods

Prior to Scheduled Spirometry, AO, and FeNO Measurement

Participants should withhold the following medications for the specified times prior to scheduled spirometry, AO, and FeNO measurement at site:

- SABAs and short-acting muscarinic antagonists for at least 6 hours. In the case of spirometry and AO post administration of study intervention, SABA should be withheld following post-BD spirometry.
- Twice daily LABA and/or LAMA-containing therapies for at least 12 hours.
- Once daily LABA and/or LAMA-containing therapies for at least 24 hours.
- LTRA for at least 24 hours.
- Twice daily theophylline for at least 12 hours.
- Once daily theophylline for at least 24 hours.

Note: for visits where in-clinic spirometry is performed post-administration of study intervention, the medications should be withheld until all spirometry assessments are complete.

Additionally, participants should withhold all BD medications for 4 hours prior to at-home spirometry assessments, where possible.

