8.1.4 Fractional Exhaled Nitric Oxide

Airway inflammation will be evaluated using a standardised single-breath FeNO test in accordance with the SOA (Table 1 and Table 2). A single exhalation technique recommended by the manufacturer will be followed (Allakhverdi et al 2007; Alving et al 2017).

The FeNO test will be performed prior to AO and spirometry. Participants should follow the relevant medication and other restrictions beforehand (Sections 6.5.3 and 5.3). If any of the above restrictions are not met, and the assessment cannot be sufficiently delayed on the day the assessment should be rescheduled within the allowed visit window.

The NIOX VERO® Airway Inflammation Monitor will be used to measure FeNO. Instructions for use of this monitor will be provided in a separate user's manual.

NIOX VERO® sensors will be replaced as recommended by the manufacturer. The vendor supplying the equipment will be responsible for ensuring that the equipment and procedures for the measurement of FeNO are validated prior to the start of the study.

If possible, all post-randomisation FeNO assessments should be performed within ± 1.5 hours of the time that the randomisation FeNO was performed.

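### Eosinophil results are withheld to protect the blind, but neither document provides for masking post-randomisation FeNO, which is measured at site before the primary spirometry

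*Protocol*

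**What the plan says.** Protocol Section 6.3.2 gives its reason for masking laboratory results: "MEDI3506 could reduce eosinophil counts in blood over time". The rule that follows from this reason is that "eosinophil, basophil, and monocyte data from the haematology laboratory tests (Table 7) will not be communicated to blinded sponsor or site personnel" for the duration of treatment and follow-up. No other result is listed as withheld.

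FeNO appears in several places, none of which mentions masking:

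- **Role.** Percent change in FeNO at Week 16 is a secondary endpoint (Protocol Section 3, Table 4). Section 4.2.1.2 says that "FeNO is a reliable quantitative tool to assess changes in asthma inflammation over time".
- **Place and timing.** Section 6.5.3 sets withhold periods "prior to scheduled spirometry, AO, and FeNO measurement at site". Table 2 schedules FeNO at SV4, SV6 to SV12 and the E/D visit.
- **Order.** When the three tests coincide, "the order should be as follows: FeNO, AO, then spirometry" (Section 1.3). Section 8.1.4 agrees: "The FeNO test will be performed prior to AO and spirometry".
- **Device.** A named "Airway Inflammation Monitor will be used to measure FeNO", and "Instructions for use of this monitor will be provided in a separate user's manual" (Section 8.1.4).
- **Analysis value.** SAP Section 3.4.7 asks for two acceptable readings, allows up to eight, and analyses the mean supplied by the vendor.

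**The concern.** The protocol accepts that a marker of drug effect can weaken the blind and acts on this for blood counts. It describes FeNO as the same kind of signal, a measure of changing inflammation, and its rationale is that the drug may reduce airway inflammation. The precaution stops short of FeNO.

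This matters because the primary endpoint, pre-bronchodilator FEV1, depends on effort and coaching, and spirometry is performed by the investigator or a delegate (Section 8.1.1.1). Investigators also have to justify calling an event an exacerbation when the eDiary criteria are not met (Section 8.1.5), and they assign causality to adverse events (Section 8.3.3). Someone who has watched FeNO fall, or not fall, over successive visits may form a view on allocation before making these measurements or judgements. A trial with 72 evaluable participants per arm, tested at a one-sided 10% level, has little room for a systematic shift in FEV1.

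**Working it through.** The central check is a comparison of text. The arithmetic only sets a scale.

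**1. What is masked.** Section 6.3.2 lists eosinophils, basophils and monocytes. FeNO is absent from that list. No masking rule for it appears in Sections 1.3, 6.5.3 or 8.1.4 of the protocol, in SAP Section 3.4.7, or elsewhere in either document.

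**2. How often FeNO precedes the primary measurement.** Table 2 has both FeNO and pre-bronchodilator spirometry at SV6, SV7, SV8, SV9 and SV10 (Weeks 1, 4, 8, 12 and 16). SV5 is a telephone contact. Four post-dose FeNO assessments therefore precede the Week 16 visit, and a fifth is taken at that visit before the spirometry. Oscillometry falls between FeNO and spirometry at all five visits, so FeNO comes earlier in the same sequence, not immediately before.

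**3. Whether any protocol rule needs the value.** FeNO is not used in:

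- the eligibility criteria (Sections 5.1 and 5.2);
- the eDiary worsening and alert criteria (Section 8.1.5);
- the treatment discontinuation criteria (Section 7.1);
- the study stopping criteria (Section 4.4.1).

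The SAP's FeNO subgroups (Section 3.1.7) use the baseline value only. Masking later values removes no protocol-defined trigger.

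**4. The plan's own figures.** Section 9.2 assumes a 150 mL difference, SD 420 mL and one-sided alpha 10%, with 72 per arm.

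- SE of one pairwise difference = 420 × √(2/72) = 70 mL.
- Power = Φ(150/70 − 1.2816) = 80.5%, which agrees with the stated figure of at least 80%.
- 216 inflated for 5% ineligible = 216/0.95 = 227.4, which rounds up to 228 as stated.

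None of these figures is disputed.

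**5. Scale of harm, as an assumption.** The documents give no size for a bias from lost blinding. If a bias of b mL favoured active drug, the one-sided type I error of one comparison would be 1 − Φ(1.2816 − b/70):

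| Assumed bias (mL) | Type I error |
|---|---|
| 0 | 10.0% |
| 10 | 12.7% |
| 20 | 16.0% |
| 30 | 19.7% |
| 50 | 28.5% |

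The table shows how sensitive the test is to a shift. It does not estimate what unmasked FeNO would cause.

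**The case against.** **Silence is not visibility.** The strongest reply is that the documents do not say FeNO is shown to anyone. Device use is left to a manual that is not part of the protocol or SAP, and the analysed value comes from the vendor. This stands as a limit: the finding is that no masking provision exists in the two documents, not that staff are known to see the readings. It does not close the gap, because Section 6.3.2 is where withheld results are listed.

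**Eosinophils have a specific basis.** Section 6.3.2 names an eosinophil effect, and Section 2.2 cites a fall in blood eosinophils with another anti-IL-33 antibody. No passage predicts a FeNO fall of any size on MEDI3506, and Section 8.5.4 says that the drug has no established pharmacodynamic measures. This is fair. A FeNO fall is a reasonable expectation from the rationale and from the choice of endpoint, but it is not a documented effect.

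**Safeguards exist.** Spirometry uses certified staff, central vendor equipment and a quality and best-test process. Exacerbations need defined treatment or hospitalisation, and events without objective support do not count. These limit the bias, but they do not hide FeNO from the person coaching the manoeuvre.

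**Stronger readings that the documents do not support.** A reader might infer any of the following.

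- *The same people do everything.* The documents do not say who runs FeNO, or that this person also coaches spirometry or judges events. Site staff involvement is inferred from measurement at site.
- *ACQ-6 and CompEx diary data are biased too.* At visits after SV1, questionnaires come first (Section 1.3), and diary variables are recorded at home by the participant (Section 8.1.8.1). An effect would require earlier FeNO values to reach the participant, which nothing shows.
- *A rate of correct guessing, measured against 50%.* With 1:1:1 allocation and two active arms, always guessing active is right for 144/216 = 66.7% of participants. Any guess rate also needs a FeNO effect and a within-person SD that the documents do not give.

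**Conclusion.** The point holds as a gap in the blinding provisions. The protocol applies a precaution to one set of inflammation-related markers and not to another that it calls reliable. The second is measured at site ahead of the primary spirometry at all five post-baseline clinic visits through Week 16, and none of the eligibility, alert, discontinuation or stopping rules depends on it. Functional unblinding is therefore possible, and the plausible routes are spirometry coaching and investigator judgement on exacerbations and adverse event causality.

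The size of any bias is unknown. The conclusion rests on three assumptions: that the unseen manual does not already mask the readings, that blinded site staff can see them, and that the drug lowers FeNO enough to be noticed. The documents do not support a claim that the blind is in fact broken or that the FEV1 result would be biased by a stated amount.

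**What to change.** In Section 6.3.2, add post-randomisation FeNO values to the results withheld from blinded site and sponsor personnel, and withhold them from participants as well. Use a masked device display or vendor-only reporting, provided that the operator still gets feedback on acceptability and repeatability, since SAP Section 3.4.7 requires two acceptable readings. Where the device cannot do this, add a site instruction that FeNO values are not shared with the investigator or with the person coaching spirometry. If the FeNO user's manual already masks the values, a cross-reference in Section 6.3.2 is enough. The change need not restrict FeNO testing done locally outside the study schedule.

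The cost is protocol wording plus a device setting, a vendor arrangement or a site instruction. Whether the device can hide values while giving repeatability feedback depends on the manual. The downside is that sites lose sight of study FeNO values during the trial. No endpoint, sample size or analysis changes.
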